### 2.2 Determination of sample size

The power is determined from expected changes in the primary endpoint of the change from baseline in pain as evaluated by the WOMAC pain sub-score. The power calculation is based on data from a 4-week double-blind diclofenac sodium 2 % topical solution treatment study in knee osteoarthritis patients (Wadsworth et al. 2016). In this study using the WOMAC LK (Likert) 3.1 scale (0-4 for each question), a decrease from baseline in WOMAC pain sub-score (5 questions) was recorded in the diclofenac treatment group of 4.5 (SD 4.5) and in the placebo group 3.6 (SD 4.2).

The estimated common SD of 4.4 in the LK 3.1 scale can be converted to a SD of 4.4 \* 2.5 = 11 in the NRS scale. Calculations based on a series of assumptions are shown below in Table **2**. With the assumptions of the SD of 11 (NRS scale), 120 subjects enrolled in each of the double-blinded treatment arms, 10 % dropout rate, normal distribution, 5 % level of significance two-sided, 80 % power, the study will be powered to detect a treatment difference in WOMAC pain sub-score between AMZ001 BID and placebo of 4.2 on the NRS scale.

WOMAC pain-subscore difference	Common SD	Power
3.8	9	0.87
	11	0.72
	13	0.57
4.0	9	0.90
	11	0.76
	13	0.61
4.2	9	0.93
	11	0.80
	13	0.66

Table 2 Power calculations for pairwise difference in WOMAC pain sub-score between AMZ001 andplacebo with 108 evaluable subjects per group, 5 % level of significance, two-sided.

The power is not adjusted for multiple comparisons and adjustment for multiplicity will not be made as there is one test only performed for the primary endpoint.

It should be noted that the current trial is not designed or powered to evaluate superiority of AMZ001 compared to Voltaren® gel, but the trial will provide important information on onset and duration of action of AMZ001 to guide future, larger trials. Also, the trial is not powered to evaluate superiority of AMZ001 applied twice daily as compared to once daily, but the trial will provide information on efficacy, safety, and tolerability of twice daily administration as compared to once daily administration.

Furthermore, the trial will be used to finalize the psychometric validation of the Pain Diary and the Satisfaction Questionnaire.

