### 4.1.1 Data presentation

All statistical tests will be performed using a two-sided test at a 5% significance level. Results from analyses will be presented with estimates, 95% confidence intervals (CIs) and p-values.

Numerical data will be presented in summary tables by number of observations (n), the number of missing values (missing), arithmetic mean, standard deviation (SD), median, first and third quartiles (Q1, Q3), minimum (min) and maximum (max) values. The mean, median, Q1 and Q3 will be reported to one decimal place more than the raw data, the standard deviation to two decimal places more than the raw data and the minimum and maximum values to the same precision as the raw data. The summary statistics presented for categorical data will be the

number of observations (n), the number of missing values (missing) and the count and percentage of subjects in each category. Number of events will also be reported where applicable.

All data will be listed by treatment group, subject and time point (if applicable). Age and sex will be displayed in all listings.

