### 4.2.1.2 Summary presentations and method of analysis

The absolute values and the absolute change from baseline in the WOMAC pain sub-score will be summarized over time by treatment group.

The primary analysis will use a restricted maximum likelihood based repeated measures mixed model (MMRM) on the dependent variable absolute change from baseline of the WOMAC pain sub-score. The analysis will include covariates of baseline value (WOMAC pain sub-score), treatment, timepoint, sex, country, the subject characteristic of unilateral/bilateral knee OA at baseline (defined by whether one or both knees meet the requirements for target knee selection) and treatment-by-timepoint interaction. An AR(1) covariance structure will be used to model the correlations between within-subject repeated measurements. The Kenward-Roger approximation will be used to estimate denominator degrees of freedom and adjust standard errors.

Sample SAS code to be used for the MMRM analysis:

```
proc mixed data=;
class treatment visit sex status subject;
model response = treatment visit treatment*visit sex country status baseline / ddfm=kr s;
repeated visit / subject=subject type=ar1;
lsmeans visit*treatment / diffs cl obsmargins;
```

run;

where *response* is the change from baseline in WOMAC pain sub-score and *baseline* is the WOMAC pain sub-score at baseline, *status* is the categorical variable of either unilateral or bilateral knee OA at baseline and *visit* is the study timepoint.

Least square mean estimates of change from baseline in WOMAC pain sub-score along with 95% confidence intervals (CI) will be presented at each time-point for each treatment group.

Estimated treatment differences at week 4 between all treatment groups along with associated 95% confidence intervals and p-values will be presented. P-values will be interpreted according to the hierarchical step-down testing procedure specified for the primary objective and also with consideration as to whether they are secondary or exploratory objectives. Model-estimated least square means and associated 95% CI of change from baseline in WOMAC pain sub-score will be plotted over time by treatment group.

The primary efficacy analysis will be based on the mITT. The robustness of the results of the primary analysis will be investigated by a sensitivity analysis based on the PP.

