Further investigation of the robustness of the primary results (in particular, the influence of time and covariates) may be performed, if deemed necessary.

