The time between baseline and first use of rescue medication will be analysed using a Cox semiparametric proportional hazards model with treatment, sex, baseline target knee WOMAC pain sub-score, country and subject characteristic of baseline unilateral/bilateral knee OA as covariates. The relative hazards and associated confidence intervals for all pairwise comparisons will be estimated from the Cox model and displayed using Kaplan-Meier curves. Frequencies and rates will be presented by treatment group. Unadjusted Kaplan Meier estimates of median 'survival' time and 95% CI will be presented by treatment group, as stated above.

If the assumptions underlying any of the pre-specified analyses are not considered appropriate for any of the endpoints once data is available, then alternate analyses may be presented.

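### The primary MMRM fixes homogeneous AR(1), so the week-4 standard error rests on one variance pooled over weeks 1 to 4; unequal visit variances would shift type I error or power

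*SAP*

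**What the plan says.** The primary endpoint is the change in WOMAC pain sub-score at week 4 (SAP 1.1.2 and 4.2.1.1). The primary model is a REML mixed model for repeated measures over weeks 1, 2, 3 and 4 with Kenward-Roger. On the covariance, SAP 4.2.1.2 says "An AR(1) covariance structure will be used to model the correlations between within-subject repeated measurements", and the sample code reads "repeated visit / subject=subject type=ar1". The code has no option for separate matrices by group and none for an empirical (sandwich) standard error. The protocol synopsis describes a repeated measures ANOVA and names no covariance structure.

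Four other provisions bear on the point:

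- **Descriptive tables.** "The absolute values and the absolute change from baseline in the WOMAC pain sub-score will be summarized over time by treatment group". SAP 4.1.1 lists the SD among the summary statistics, so SDs by visit will be produced. SAP 2.3 and 6 provide for drafts with dummy treatment groups.
- **Committed sensitivity analysis.** "The robustness of the results of the primary analysis will be investigated by a sensitivity analysis based on the PP". This changes the analysis set and names no other model.
- **Optional work.** "Further investigation of the robustness of the primary results (in particular, the influence of time and covariates) may be performed, if deemed necessary". SAP 4.2.2.2 adds that if assumptions look inappropriate "for any of the endpoints once data is available, then alternate analyses may be presented". Neither sentence names a covariance structure.
- **Planning SD.** "The estimated common SD of 4.4 in the LK 3.1 scale can be converted to a SD of" 11 (SAP 2.2). Table 2 also tries 9 and 13.

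**The concern.** Homogeneous AR(1) has two parameters: a variance shared by all four visits and a correlation that decays with lag. The text presents it as a model for correlations, but it also imposes equal variances over time, and the SAP gives no reason to expect that.

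The constraint matters because inference is at a single visit. The model-based standard error of the week-4 difference is driven by the fitted common variance, which is close to an average over weeks 1 to 4. Kenward-Roger adjusts degrees of freedom and small-sample standard errors within the assumed structure. It does not repair a wrong one. The 5% level and 80% power at week 4 therefore hold only if the week-4 variance is close to the pooled value.

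**Working it through.** **Inputs from the SAP.** Two-sided 5% level (4.1.1). Difference 4.2, SD 11, 120 per arm, 10% dropout, 108 evaluable per arm (2.2). Four post-baseline visits (4.2.1.1).

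**Assumed, because the documents do not give them.** SDs of change at each visit, all ending at 11 in week 4, and six true within-subject correlation patterns: AR(1) 0.6 and 0.8, exchangeable 0.5, 0.7 and 0.8, and Toeplitz (0.8, 0.7, 0.65).

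**Step 1: the plan's own figures.** The common SD is √((4.5² + 4.2²)/2) = 4.35, which the SAP gives as 4.4; 4.4 × 2.5 = 11. The standard error at week 4 is 11 × √(2/108) = 1.497, and 4.2/1.497 = 2.806. Power = Φ(2.806 − 1.960) = 0.801, against the stated 0.80. All nine cells of Table 2 reproduce within one percentage point.

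**Step 2: what AR(1) estimates.** With true covariance S0, the fitted AR(1) matrix S tends to the one minimising log|S| + tr(S⁻¹S0). Let R = fitted SD / true week-4 SD. Then

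- type I error = 2 × (1 − Φ(1.96 R))
- power = Φ(2.806 − 1.96 R)

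**Step 3: by hand.** For linear profiles the fitted SD is almost exactly the root mean square of the four SDs.

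- 9.9, 10.27, 10.63, 11: root mean square 10.46, R = 0.951, type I error = 2 × (1 − Φ(1.863)) = 6.2%.
- 13, 12.33, 11.67, 11: root mean square 12.02, R = 1.093, type I error = 2 × (1 − Φ(2.142)) = 3.2%, power = Φ(0.663) = 0.75.

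**Step 4: full minimisation over the six correlation patterns.** Uneven profiles depend slightly on the pattern, hence the ranges.

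| Assumed SDs, weeks 1-4 | Type I error | Power |
|---|---|---|
| 11/11/11/11 | 5.0% | 0.80 |
| 10/12/11/11 | 5.1-5.4% | |
| 10.5/10.8/11/11 | 5.4% | |
| 10/11/11/11 | 5.6-5.8% | |
| linear 9.9 to 11 | 6.2% | |
| linear 8.8 to 11 | 7.6-7.7% | |
| 11.5/11.3/11.1/11 | 4.5% | |
| linear 12.1 to 11 | 3.9% | 0.77 |
| linear 13 to 11 | 3.2% | 0.75 |

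Power is left blank where type I error is above 5%, because the apparent gain comes from the inflation. With equal SDs type I error stays at 5.0% under every correlation pattern, so the equal-variance constraint drives the effect. Rates are the same on the 0-100 scale.

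**Step 5: simulation of AR(1) against unstructured.** Three arms of 120, four visits, the planned covariates, 10% monotone random dropout, REML, and a t reference with 345 (AR(1)) or 330 (unstructured) df in place of exact Kenward-Roger. Unequal-SD runs use exchangeable correlation 0.7. Null rejection rates, batches shown separately:

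| Profile | Trials | AR(1) | Unstructured |
|---|---|---|---|
| 10.5/10.8/11/11 | 4,000 | 5.3% | 4.6% |
| 9.9 to 11 | 4,000 | 6.5% | 5.5% |
| 9.9 to 11 | 6,000 more | 6.0% | 4.7% |
| 8.8 to 11 | 4,000 | 8.4% | 6.1% |
| 8.8 to 11 | 12,000 more | 7.4% | 4.9% |
| 13 to 11 | 4,000 | 3.2% | 5.3% |

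For 13 to 11, power was 0.75 under AR(1) and 0.82 under unstructured. The two unstructured batches for 8.8 to 11 differ by 1.2 points, about 3 standard errors, with no explanation found; pooled they give 5.2%. The mild profile (margin ±0.7 points) cannot be told apart from 5%. A separate simulation of AR(1) alone gave 5.0-5.4% with equal SDs, 6.4% for 10 to 11, 7.5% for 9 to 11, and 3.3-3.4% with power 74-76% for 13 to 11.

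**Step 6: cost with equal SDs.** Paired power difference, unstructured minus AR(1): +0.004 (±0.005) for exchangeable 0.7, +0.001 (±0.004) for AR 0.6, 0.000 (±0.004) for Toeplitz.

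**The case against.** A pre-specified AR(1) is a legitimate choice, and nothing in the documents shows unequal variances. The larger effects need the SD to move by about 2 points between weeks 1 and 4, and mild profiles stay within 4.5-5.8%. All of this stands, and it limits the point to a conditional one.

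A reader might infer that unequal variances could come to light only after the result is known. The documents do not support that. The dummy-treatment drafts in SAP 2.3 and 6 can show SDs by visit before true allocation is revealed, and the optional clauses would permit a response. What remains is that no rule and no alternative covariance is tied to those tables, so any response would be discretionary.

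The simulations are also weaker on practicability than they look. All 46,000 unstructured fits converged, but each started from the true matrix, so they say little about convergence in practice. Only a four-visit design with 3 × 120 subjects was tested. With two post-baseline visits, unstructured, heterogeneous Toeplitz and heterogeneous AR(1) are the same model, so that fallback order is empty for the chair-stand test and EQ5D VAS.

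A milder remedy is to keep AR(1) and add one pre-specified sensitivity analysis with visit-specific variances. That would help, but the primary p-value would still rest on the constraint.

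**Conclusion.** The point holds as a conditional weakness that is cheap to remove. It is certain that the text and code impose one variance over weeks 1 to 4, that the week-4 inference uses it, and that Kenward-Roger does not correct it. The size is not known. Under the assumed profiles ending at 11, type I error ranges from 3.2% (power 0.75) to 7.7%, and is close to 5% when differences are mild.

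A reader might go further and conclude that this trial's type I error is inflated. The documents do not support that: they give no SD by visit, and the opposite direction is equally open. The 9 and 13 in Table 2 are alternative common SDs, not values at different visits, and the common SD of 4.4 is common to two arms of another study, not to visits. Nor does the point challenge the treatment estimate, the sample size or Table 2.

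**What to change.** In the SAP 4.2.1.2 text and code:

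- **Primary analysis and other endpoints with four post-baseline visits (WOMAC scores, PGA, ICOAP).** Replace `type=ar1` with `type=un` and keep Kenward-Roger. Pre-specify heterogeneous Toeplitz, then heterogeneous AR(1), to be used in that order and only on non-convergence.
- **Two post-baseline visits (chair-stand, EQ5D VAS).** Use `type=un`. Any fallback must be a simpler structure, such as one common variance with one correlation.
- **WPAI (three post-baseline visits, fewer subjects for the work items).** Use `type=un` with the same fallback order, noting that performance there was not tested.

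The cost is a few lines of SAP text and code. With four visits, the model has 4 variances + 6 correlations = 10 covariance parameters instead of 2, and it may fail to converge, which is why the fallback is needed. About 360 double-blind subjects should support this, and no power loss was visible in the three equal-SD settings, though that is not a general proof. The unstructured model still assumes one matrix for all arms. The protocol synopsis names no covariance structure and needs no change; the full protocol's statistical section was not available here and should be checked.

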## 1 Synopsis

Clinical Trial Protocol Number	AMZ001-006
Title	A placebo-controlled, double-blind, randomized, trial of Diclofenac Gel AMZ001 3.06 % for the treatment of knee osteoarthritis symptoms
Trial Phase	2/3
IND Number	116375
FDA covered trial	Yes
EudraCT Number	2018-001934-16
Sponsor	Amzell BV Chief Scientific Officer Name: [name] Address: [name]
Sponsor Legal Representative in the European Union	Amzell BV [name] [contact]
Trial centers/countries	Denmark Czech Republic United States of America
Planned trial period        (first subject in-last subject out)	First subject in: August 2018 Last subject out: March 2019
Objectives: Primary Objective	
 
To evaluate changes in pain intensity, in terms of the WOMAC pain score of the target knee
 

Protocol ID  
AMZ001-006  
Version 1.2

22NOV2018

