## 2.4 Randomization

The screening/randomization procedure will be centrally managed through an electronic Interactive Web Responding System integrated in the eCRF.

Eligible subjects will be randomized to one of four treatment groups with an allocation ratio of 3:3:3:2. Each of the three double-blinded treatment groups (AMZ001 BID, AMZ001 QD and placebo) will be randomized with approximately 120 subjects for the primary objective of assessment of an analgesic effect of topical AMZ001 gel compared with placebo. The single-blinded group of the comparator of Voltaren® gel 1 % will be randomized with approximately 80 subjects.

Randomization will be stratified by country to ensure balance of treatment groups with respect to intrinsic and extrinsic factors that may affect the OA outcomes.

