#### 4.2.2.2 Summary presentations and methods of analysis

All summaries and statistical analysis for the secondary endpoints will be performed for the mITT set only.

For the following continuous secondary endpoints, absolute values and absolute change from baseline will be summarised over time by treatment group. Statistical analysis and hypothesis testing will be conducted as for the primary efficacy analysis using a mixed effects repeated measures model with data from double-blind treatment groups only.

- WOMAC total score
- WOMAC function score
- WOMAC stiffness score
- WOMAC pain weight bearing score
- WOMAC pain non-weight bearing score

- Patient Global Assessment (PGA)
- ICOAP total OA pain score
- ICOAP constant OA pain score
- ICOAP intermittent OA pain score
- Chair stand test, number of repetitions

The number of subjects using any rescue medication (i.e. at least one tablet), the total dose of rescue medication (g), and the average dose of rescue medication per day on study drug (g/day) will be summarized by treatment group. Time to first use of rescue medication will be summarised by unadjusted Kaplan Meier estimates of median time to first use of rescue medication with 95% CI. For subjects not taking any rescue medication, the total dose of rescue medication will be set to 0 mg and time to first use of rescue medication will be censored at the Visit 6/EOT visit date or the last date of subject participation in the study if this is not available.

The average dose of rescue medication per day on study drug will analysed using an analysis of covariance model with treatment, sex, baseline target knee WOMAC pain sub-score, country and subject characteristic of baseline unilateral/bilateral knee OA as explanatory variables. Least square mean estimates of each dependent variable along with 95% confidence intervals (CI) will be presented for each treatment group. Estimated treatment differences between all treatment groups along with associated 95% confidence intervals and p-values will be presented.

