### 4.2.3.2 Summary presentations and methods of analysis

Summaries and analysis will be performed for the mITT set only.

For the following QoL endpoints, absolute values and absolute change from baseline will be summarized over time by treatment group. Statistical analysis will be conducted as for the primary efficacy analysis using a mixed effects repeated measures model.

- WPAI % time missed
- WPAI % impairment while working
- WPAI % overall work impairment
- WPAI % activity impairment
- EQ5D VAS

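### The primary MMRM code puts country in MODEL but not in CLASS, so the three-country randomisation stratum would be fitted as one slope on arbitrary codes, or the step would stop

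*SAP*

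**What the plan says.** The text of SAP 4.2.1.2 names country among the covariates of the primary MMRM, without saying whether it is categorical. The section then gives sample SAS code that it says the analysis will use. The two statements that matter are:

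- CLASS: "class treatment visit sex status subject"
- MODEL: "model response = treatment visit treatment*visit sex country status baseline / ddfm=kr s"

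The notes under the code explain response, baseline, status and visit. Status "is the categorical variable of either unilateral or bilateral knee OA at baseline". Country is not explained.

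SAP 2.4 makes country the stratum: "Randomization will be stratified by country to ensure balance of treatment groups with respect to intrinsic and extrinsic factors". The protocol synopsis lists three countries: "Denmark Czech Republic United States of America". The model in the synopsis has no country term, so the SAP is the only place where this term is specified.

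The model is reused. For the ten continuous secondary endpoints, SAP 4.2.2.2 says: "Statistical analysis and hypothesis testing will be conducted as for the primary efficacy analysis using a mixed effects repeated measures model". For the five quality-of-life endpoints, SAP 4.2.3.2 says: "Statistical analysis will be conducted as for the primary efficacy analysis using a mixed effects repeated measures model". The per-protocol sensitivity analysis of the primary endpoint is also based on it.

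**The concern.** A variable that is in MODEL but not in CLASS is treated by PROC MIXED as continuous. For a nominal variable with three levels there are two possible outcomes, and the documents do not say how country is stored.

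- **Numeric codes.** The model fits one slope across the codes. The country adjustment, and with it the SE and p-value of the treatment comparison, then depends on an arbitrary numbering. The run produces no error.
- **Text values.** The step stops, and the code has to be changed after the SAP is final.

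At stake is the precision of the primary comparison and the principle that a pre-specified p-value should not depend on code order. Bias is not at stake. Stratified allocation keeps the arms balanced by country, and the slope still removes the linear part of any country differences.

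**Working it through.** **1. The plan's own power figure.** SAP 2.2 states: "With the assumptions of the SD of 11 (NRS scale), 120 subjects enrolled in each of the double-blinded treatment arms". It also assumes 10% dropout, a two-sided 5% level and a difference of 4.2. Evaluable subjects: 120 × 0.90 = 108 per arm. SE = 11 × √(2/108) = 1.497, and 4.2/1.497 = 2.806. Power = Φ(2.806 − 1.960) = 0.801; the noncentral t with 214 df gives 0.798. The stated 0.80 is reproduced. That calculation uses no country term, so it is unaffected.

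**2. CLASS against MODEL.**

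| MODEL term | In CLASS? | Nature |
|---|---|---|
| treatment, visit | yes | nominal |
| sex | yes | nominal |
| status | yes | nominal |
| country | **no** | nominal, 3 levels |
| baseline | no | continuous |

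Only country is misplaced. Three levels need 3 − 1 = 2 df; a slope has 1. (The behaviour of PROC MIXED is standard; SAS was not run for this check.)

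**3. Variance left in the residual.** The documents give no country effects or shares. Assumptions: equal shares, codes 1, 2, 3, residual SD 11 (variance 121) on the 0-50 scale. Let *v* be the between-country variance that the slope misses. The SE ratio, slope to factor, is √((121 + *v*)/121). Normalising to 0-100 doubles everything and leaves the ratios unchanged.

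| Country means at codes 1, 2, 3 | *v* | SE ratio |
|---|---|---|
| 0, d, 0 (slope = 0) | 2d²/9 = 2.0 (d = 3); 5.56 (d = 5) | 1.008; 1.023 |
| 0, 0, d (slope = d/2) | 2d²/9 − d²/6 = d²/18 = 0.50; 1.39 | 1.002; 1.006 |
| 0, 2.5, 5 coded in order | 0 | 1.000 |
| 0, 2.5, 5 coded out of order | 75% of 4.17 = 3.12 | 1.013 |

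The last two rows are the same data with different numbering.

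**4. Operating characteristics.** Simulation of week 4 only: three arms of 108, 36 per arm in each country, residual SD 11, difference 4.2, linear model with treatment and country, 40,000 trials per cell, country means 0, d, 0.

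| d | Mean SE, slope / factor | Power, slope / factor | Type I error, slope / factor |
|---|---|---|---|
| 3 | 1.509 / 1.496 | 0.794 / 0.799 | 0.049 / 0.051 |
| 5 | 1.530 / 1.496 | 0.785 / 0.798 | 0.045 / 0.049 |

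The mean treatment estimate is the same under both codings (−4.19 for d = 3, −4.20 for d = 5). The type I error at d = 5 can be confirmed by hand. The true variability of the estimate is unchanged while its estimated SE is inflated, so the error rate is 2 × (1 − Φ(1.960 × 1.023)) = 0.045, which is conservative.

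A separate simulation of the same kind (4,000 trials per scenario) agrees:

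- Middle country shifted by 4 points: power 0.786 with the slope against 0.794 with the factor.
- Middle country shifted by 8 points: 0.760 against 0.798.
- Means 0, 4, 8 coded in order: no difference. Coded out of order: 0.784 against 0.804.
- No country effect: no difference.

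**5. If SD 11 is the total SD rather than the residual SD.** In the pattern 0, d, 0 the slope removes nothing and power stays at 0.798. The factor lowers the residual SD to √(121 − *v*) = 10.91 (d = 3) or 10.74 (d = 5), giving power 0.804 or 0.816. On this reading the slope forgoes a gain and does not fall below plan.

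**The case against.** The strongest reply is that this is a slip in illustrative code. The prose is the specification, and it lists country beside sex and unilateral/bilateral status, which any statistician would read as a factor. That only status is called categorical proves little, since sex and treatment are not called so either. If country is stored as text, the step stops, someone adds it to CLASS, and the intended model runs.

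There are also safeguards. SAP 5 requires parallel programming by an independent statistician for the efficacy analyses. SAP 6 adds draft outputs with dummy treatments, a review meeting and a second delivery under full QC. The `s` option prints the fixed-effect solution, where a single country coefficient could be noticed. Finally, every non-zero loss rests on assumed country effects in a one-visit simplification of the planned MMRM, and even these losses are small.

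Most of this stands: a factor was probably intended, detection is quite likely, and the effect is small. It does not remove the point. The SAP presents the code as what the analysis will use, and no sentence anywhere states that country is categorical. Two programmers who both copy the printed CLASS line will agree with each other and repeat the slip. If one of them corrects it silently, the primary analysis departs from the printed code without a record.

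**Conclusion.** The concern holds. The printed code for the primary model is wrong for a three-level nominal stratum, and the continuous secondary and quality-of-life models inherit it.

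No material bias is expected, and the type I error is if anything slightly conservative. Where the slope captures none of a 3- or 5-point country difference, the SE is 0.8% or 2.3% larger and simulated power falls by 0.005 or 0.013. In milder patterns the SE increase is 0.2% to 0.6%, and with differences linear in the codes it is nil. Code order alone can move the SE by 1.3%. These figures assume equal country shares, SD 11, 108 per arm and country differences that the documents do not give.

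This does not threaten the trial's conclusion. It should still be corrected before unblinding, because the primary p-value should not depend on how countries are numbered.

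**What to change.** In SAP 4.2.1.2, change the statement to `class treatment visit sex country status subject;` and add a clause saying that country enters the model as a three-level categorical covariate. The secondary and quality-of-life MMRMs then follow by reference. The rescue-medication ANCOVA and Cox models print no code, so nothing there needs correcting.

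The cost is one word, one clause and one extra model degree of freedom among about 360 (3 × 120) subjects in the double-blind groups.
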